5.1. Inclusion Criteria

A subject will be eligible for inclusion in this study only if all of the following criteria apply:

| AGE |
|--|
| 1. ≥ 18 years of age and provided signed written informed consent |

| TYPE OF SUBJECT AND DIAGNOSIS INCLUDING DISEASE SEVERITY |
|---|
| 
2. Subjects must have IPSS-R high or very high risk myelodysplastic syndromes (MDS) by WHO classification
 
3. Subjects must have failed hypomethylating treatment where “failure” is defined as:
 
 a) Progression (according to 2006 IWG criteria) at any time after initiation of the hypomethylating treatment OR b) Failure to achieve complete or partial response or hematological improvement (HI) (according to 2006 IWG) after at least 4 cycles treatment OR c) Relapse after initial complete or partial response or HI (according to 2006 IWG criteria). 
4. Subjects are not a candidate, or have failed allogeneic stem cell transplantation. Subjects who underwent allo-transplant in the past are eligible under following conditions:
 
 a) transplant was ≥ 2 year prior to enrolment, and b) no evidence of active GVHD 
5. Eastern Cooperative Oncology Group (ECOG) performance status of 0-1.
 
6. Subjects must have a life expectancy of at least 12 weeks, in the opinion of the investigator.
 
7. Able to swallow and retain orally administered medication and does not have any clinically significant gastrointestinal abnormalities that may alter absorption such as malabsorption syndrome or major resection of the stomach or bowels.
 
8. All prior treatment-related toxicities must be National Cancer Institute- Common Toxicity Criteria for Adverse Events (NCI-CTCAE), version 4.0 \leq Grade 1 at the time of enrollment (except for alopecia).
 |

LABORATORY

9. Adequate baseline organ function defined by:

| System | Laboratory Values |
|--|--|
| Coagulation | |
| INR and aPTT | ≤1.3 X ULN |
| Hematologic | |
| PLT | ≥10,000 (transfusions permitted to bring platelet count to >10,000) |
| Hepatic | |
| Total bilirubin | ≤ 1.5 X ULN ^a |
| ALT | ≤2.5 × ULN |
| Renal | |
| Creatinine | ≤1.5 X ULN |
| OR | |
| Calculated creatinine clearance by Chronic Kidney Disease Epidemiology Collaboration (CKD-EPI) equation (Appendix 3) or measured from 24hr urine | ≥ 50 mL/min |
| Cardiac | |
| Ejection fraction | ≥ LLN by Echocardiogram (ECHO) or MUGA |

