5.5. Safety Management

5.5.1. Events of Special Interest

5.5.1.1. Hematologic Events

Any signs of bleeding, bruising and infection will be monitored closely throughout the study. Platelet transfusion will be administered following institutional guidelines and practices. Neutropenia and anemia management and fungal or bacterial prophylaxis will also follow institutional guidelines.

Transfusions are allowed throughout the study as clinically indicated.

Erythropoietin is not allowed on study.

The use of granulocyte stimulating growth factors is only allowed for treatment of febrile neutropenia and other life threatening infections.

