9.1.2. Part 2: Disease-Specific Expansion Cohorts

The primary goal of Part 2 is to evaluate disease-specific clinical activity in subjects with GSK2879552, alone or in combination with azacitidine, in adult subjects with MDS. Clinical activity is defined as a clinical benefit rate (% of subjects achieving CR, PR, HI or SD [per 2006 IWG criteria]). This will be conducted by testing the null hypothesis that $P_0 \leq 0.3$ versus the alternative that $P_1 \geq 0.5$, Subjects in Part 1 and Part 2 treated with the same starting dose will be analyzed together.

The Part 2 portion of the study will employ a Bayesian predictive adaptive design [Lee, 2008] for Arm A and Arm B separately that allows the trial to be monitored more frequently at multiple stages. The criteria will be based on a historically unimportant response rate of 30% versus a response rate of interest of 50%. Bayesian statistics will be employed to calculate the predictive probability that the response rate $\geq 50\%$ and $\geq 30\%$ at interim assuming a Beta prior for the Binomial distributed data. Predictive probability calculates the probability that the response rate $\geq 50\%$ or $\geq 30\%$ at the end of Part 2 given the responses that are currently being observed at interim. It predicts what is likely to happen at the end of Part 2 so it is more meaningful and straightforward than posterior probability. A weak prior Beta (0.005, 0.005) is used, which is equivalent to the information present in 0.01 subjects. The first interim analysis may be conducted when at least 10 subjects are recruited for each Arm. Futility interim analysis decision rules for the 10th to 28th evaluable subjects, specifying the number of subjects with clinical activity (CR, PR, HI or SD) needed for continuing enrolment or stopping for futility when total sample size is up to 28, is presented in Table 5. These rules are intended as a guideline. Actual decisions will depend on the totality of the data.

Table 5 Decision Making Criteria for Futility

| Number of Evaluable Subjects | ≤ This Number of Responses to Stop Early for Futility | Probability of continuing enrolling when CBR=0.3 | Probability of continuing enrolling when CBR=0.5 |
|------------------------------|---|--|--|
| 10 | 1 | 0.8507 | 0.9893 |
| 12 | 2 | 0.7363 | 0.9783 |
| 14 | 3 | 0.6242 | 0.9655 |
| 16 | 3 | 0.6242 | 0.9655 |
| 18 | 4 | 0.5739 | 0.9620 |
| 20 | 5 | 0.5087 | 0.9566 |
| 22 | 6 | 0.4414 | 0.9500 |
| 24 | 8 | 0.2601 | 0.9103 |

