| 26 | 9 | 0.2059 | 0.8927 |
| 28 | 11 | 0.0000 | 0.0000 |

For the separate interim looks in each cohort in Part 2, the enrollment for that cohort may be stopped due to futility if the predictive probability that the confirmed response rate $\geq 30\%$ (historical control) is small (e.g., less than a 2% chance for a total sample size of 28 subjects). Enrollment may also be stopped due to futility if the equivalent of less than 2 responses is observed in the first 10 enrolled evaluable subjects in that cohort or less than 3 responses are observed in the first 12 evaluable subjects. The evaluable subject is defined as a subject, who has either progressed, withdrew from the study, was lost to follow-up, or is ongoing and has completed at least one post treatment disease assessment. For example, when there are 10 evaluable subjects available at the time of interim analysis with only one response, then the Arm may be stop for futility. Otherwise, the enrolment of the respective Arm will continue to the target sample size.

When the total sample size in a treatment arm is 28 and at least 12 responders out of 28 subjects are observed, we can claim null hypothesis is rejected.

No formal hypotheses are set up to compare the activity between Arm A and Arm B. The CBR and ORR will be reported for both arms separately at the end of Part 2.

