12.10. Appendix 10: IWG CRITERIA FOR RESPONSE

| Category | Response Criteria |
|------------------------------|--|
| Complete Remission | Bone marrow: $\leq 5\%$ myeloblasts with normal maturation of all cell linesa Persistent dysplasia will be noteda,b Peripheral blood (Response must be maintained for at least 4 weeks) Hgb ≥ 11 g/dL Platelets ≥ 100 Gi/L Neutrophils ≥ 1.0 Gi/Lb Blasts 0% |
| Partial Remission | All CR criteria if abnormal before treatment except: Bone marrow blasts decreased by $\geq 50\%$ over pre-treatment but still $> 5\%$ Cellularity and morphology not relevant |
| Marrow CR^b | Bone marrow: $\leq 5\%$ myeloblasts and decrease by $\geq 50\%$ over pre-treatment ^b Peripheral blood: if HI responses, they will be noted in addition to marrow CR ^b |
| HI | Erythroid (HI-E): hgb increase of > 1.5 g/dL decrease of $>$ RBC transfusions/8weeks versus pretreatment requirement in previous 8 weeks; only RBC transfusions given for a pretreatment Hgb of < 9.0 g/dL count Platelet (HI-P): increase of $> 30,000$ /mL (starting with $> 20,000$ /mL) increase from $< 20,000$ /mL to $> 20,000$ /mL by $> 100\%$ Neutrophil (HI-N): increase of $> 100\%$ and > 500 /uL |
| Stable Disease | Failure to achieve at least PR, but no evidence of progression > 8 wks |
| Disease Progression | For subjects with: 
 • Less than 5% BM blasts: $\geq 50\%$ increase in blasts to $> 5\%$ blasts • 5%-<10% BM blasts: $\geq 50\%$ increase to $> 10\%$ blasts • 10%-<20% BM blasts: $\geq 50\%$ increase to $> 20\%$ blasts • 20%-30% BM blasts: $\geq 50\%$ increase to $> 30\%$ blasts Any of the following: 
 • At least 50% decrement from maximum remission/response in granulocytes or platelets • Reduction in Hgb by ≥ 2 g/dL • Transfusion dependence |
| Non-evaluable | Subject does not meet any of the above criteria |

BM = bone marrow ; CR = complete remission; Hgb = hemoglobin;; PR = partial remission

a. Dysplastic changes should consider the normal range of dysplastic changes (modification).

b. Modification to IWG response criteria [[Cheson, 2006](#)].

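### Appendix 10: the count-based limbs of HI need no duration and do not exclude transfused or G-CSF-supported counts, and transfusion dependence is progression without reference to baseline

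*Protocol*

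**What the plan says.** Protocol section 7.4 sends the reader to Appendix 10 for the response criteria. There:

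- Complete remission carries a maintenance condition: "Response must be maintained for at least 4 weeks". Stable disease needs more than 8 weeks without progression.
- The transfusion limb of erythroid HI compares "RBC transfusions/8weeks versus pretreatment requirement in previous 8 weeks; only RBC transfusions given for a pretreatment Hgb of" less than 9.0 g/dL. It has both a time window and a rule on which transfusions count.
- The other HI limbs are count changes only. Haemoglobin must rise by more than 1.5 g/dL. Platelets must rise by more than 30,000 from a start above 20,000, or from below to above 20,000 by more than 100%. Neutrophils must rise by more than 100% and by more than 500. No duration, repeat count or support-free interval is stated.
- Disease progression includes, among items any one of which suffices, "Transfusion dependence". Nothing says that it must be new.

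On supportive care, section 5.5.1.1 states "Transfusions are allowed throughout the study as clinically indicated" and "The use of granulocyte stimulating growth factors is only allowed for treatment of febrile neutropenia and other life threatening infections"; it prohibits erythropoietin. For the entry platelet count, section 5.1 has "transfusions permitted to bring platelet count to >10,000". Section 3.2 makes CBR and ORR the Part 2 primary endpoints, with HI in both, and records transfusions in the 3 months before entry. Section 9.4.1 counts HI or stable disease towards CBR whenever it occurs.

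**The concern.** A count raised by a transfusion, or by G-CSF given for an infection, reflects supportive care and not disease activity. Under the HI count limbs one such value on an assessment day makes the subject a responder for both primary endpoints. The trial is open-label, transfusion is unrestricted, and thrombocytopenia is the drug's main toxicity, so transfused platelet counts are to be expected.

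The progression item errs the other way. A subject already dependent at entry has, on a literal reading, progressed at the first assessment and cannot reach stable disease. The same call shortens PFS, and it bears on stopping treatment (section 4.7) and on access to crossover (section 4.6).

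The success rule is 12 of 28 per arm, so a few misclassified subjects can decide an arm.

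**Working it through.** **Check of the wording**

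| Item in Appendix 10 | Time condition | Rule on transfusion or G-CSF |
|---|---|---|
| Complete remission | 4 weeks | not stated |
| Stable disease | more than 8 weeks | not stated |
| HI-E, transfusion limb | 8 weeks against previous 8 | only transfusions below an Hgb level count |
| HI-E, haemoglobin limb | none | none |
| HI-P | none | none |
| HI-N | none | none |
| Transfusion dependence as progression | none | no baseline reference |

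Example for HI-P: 12,000 transfused to 26,000 is a rise of 14,000/12,000 = 117%, from below to above 20,000. Both conditions of the second platelet limb are met.

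**The plan's own figures**

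Inputs from sections 9.1.2 and 9.2.1: "The criteria will be based on a historically unimportant response rate of 30% versus a response rate of interest of 50" per cent; a maximum of 28 subjects; success when "at least 12 responders out of 28 subjects are observed, we can claim null hypothesis is rejected"; stated type I error 0.099 and power 81%. Table 5 stops for futility at or below 1/10, 2/12, 3/14, 3/16, 4/18, 5/20, 6/22, 8/24, 9/26 and 11/28 responses.

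An exact binomial recursion, adding one subject at a time and keeping only paths above each boundary, matches Table 5 to four decimals at every look from 10 to 26. It gives:

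- P(at least 12 of 28 after all looks) at 30%: 0.0991 (stated 0.099)
- the same at 50%: 0.8174 (stated 81%)
- without interim looks: 0.1028 and 0.8275

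**Illustration of misclassification**

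The document gives no rate for either error, so f and d below are assumptions.

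(a) A fraction f of subjects without true benefit is scored HI. Observed CBR = 0.30 + 0.70f.

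| f | Observed CBR | P(success), true CBR 30% |
|---|---|---|
| 0 | 0.300 | 0.099 |
| 5% | 0.335 | 0.19 |
| 10% | 0.370 | 0.31 |
| 15% | 0.405 | 0.46 |

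(b) A fraction d of subjects with true benefit is scored progressed and loses benefit status. Observed CBR = 0.50(1 − d).

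| d | Observed CBR | P(success), true CBR 50% |
|---|---|---|
| 0 | 0.50 | 0.82 |
| 10% | 0.45 | 0.65 |
| 20% | 0.40 | 0.44 |
| 30% | 0.35 | 0.24 |

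(c) Both together, with true rate t: observed CBR = t(1 − d) + (1 − t)f.

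- f = 10%, d = 20%: 0.31 at t = 0.30 and 0.45 at t = 0.50, so the error rate is 0.12 and power 0.65.
- f = 20%, d = 20%: 0.38 and 0.50, so the error rate is 0.35 and power 0.82.

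The errors oppose each other but do not in general restore the planned pair of figures.

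**The case against.** The strongest reply is that Appendix 10 summarises the 2006 IWG criteria, which the endpoints cite, and that derivation detail can go to the Reporting and Analysis Plan. Whether that source supplies a duration or a baseline rule cannot be checked here. The reply does not cure the problem. Investigators apply Appendix 10 as the trial runs, and their calls feed futility looks from 10 subjects as well as discontinuation and crossover, which a later analysis document cannot undo. As it reads here, neither the HI row nor the progression row is marked as a modification. Section 9.4.1 points to Appendices 5 and 6 for the criteria, but those cover adverse events and ECOG status, so Appendix 10 is the only operative text. Section 9.1.2 mentions a confirmed response rate and section 7.4 a marrow to confirm response; neither says how HI is confirmed.

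Other objections stand and limit the point:

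- A reader might infer that HI as a whole has no duration. The HI-E transfusion limb shows otherwise.
- A reader might infer that growth factors in general can produce HI. Erythropoietin is prohibited and G-CSF is restricted, so only HI-N is exposed. The neutrophil rebound after dosing stops is reported in rats and dogs (section 2.2.3.2), not in humans.
- The HI-E transfusion threshold seems to lack its number. That may be lost text and is not counted as a fault.
- Platelet transfusion to meet an entry threshold is not itself dependence, a term the protocol does not define. The neighbouring count items describe changes, so an assessor may well read this one as a change too. The wording does not require it.

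**Conclusion.** The point holds in this form: three count-based HI limbs lack a duration and a support-free condition, and the transfusion-dependence item lacks a baseline reference. Followed as written, both rules can misclassify the primary endpoint.

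The size is unknown. The tables assume that each false HI falls on someone who would not otherwise reach stable disease or better, and that each false progression removes benefit altogether. The second is severe, because a response at any time would still count for CBR. For ORR, where stable disease does not count, false HI inflates the rate more directly. A reader might take 0.31 or 0.44 as the trial's real error rate or power; the documents do not support that, nor a claim about which error dominates. The figures show only that a rule of 12 in 28 is sensitive to modest misclassification.

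**What to change.** For endpoint derivation, state in Appendix 10 that the haemoglobin, platelet and neutrophil limbs of HI count only if sustained for a stated minimum period, on counts not supported by recent transfusion (haemoglobin, platelets) or G-CSF (neutrophils). The 8 weeks already used for stable disease and the HI-E transfusion limb is one candidate. The sponsor should define what counts as recent, since the protocol offers no interval.

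Reconcile the transfusion-dependence item with sections 3.2, 4.6, 4.7, 5.1 and 5.5.1.1, so that for the endpoint it is judged against the recorded baseline transfusion requirement. Because progression also governs discontinuation and crossover, the consequences there are for the sponsor to settle; no clinical rule is proposed here.

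The cost is appendix wording. Transfusion need, concomitant medication and blood counts are already collected. HI would be confirmed later and ORR may be lower. As already holds for stable disease, a subject with only one 4-week assessment could not yet count as HI, which the futility looks would have to allow for.

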2.2.4. Pharmacokinetics and Pharmacodynamics of GSK2879552 in Human

GSK2879552 pharmacokinetics (PK) are characterized by a rapid absorption with maximum concentration occurring typically within the first hour after dosing. GSK2879552 is eliminated slowly with an average terminal phase half-life of 12 to 38 hours, leading to a moderate accumulation following once daily oral administration.

Following single and repeated once daily administration of 0.25 mg to 4 mg of GSK2879552, C_{max} and AUC tended to increase in a dose proportional fashion.

As LSD1 inhibition results in a blockage of platelet maturation, platelet count changes can be viewed as a PD effect and was evaluated in subjects with small cell lung cancer (study 200858). Following daily administration of 3 mg in 3 subjects, the median lowest platelet count was 10 G/L (range: 9 to 15), observed between Day 15 and Day 18. The median platelet nadir was 29 G/L (range: 22 to 93) in the 5 subjects who received 2 mg of GSK2879552 once daily. There is a steep relationship between platelet nadir and GSK2879552 dose, C_{max} , or AUC. Following GSK2879552 dose interruption, platelet count started to recover within days with full recovery seen after a week interruption. But platelet count decreased once again, with a delay, following treatment restart.

Based on preclinical data, it is predicted that an increase in CD11b- and CD86-positive AML blasts will be consistent with a pro-differentiation mechanism and/or target engagement in subjects with AML (study 200200). Using 10% additional CD11b or CD86 positive blasts in treatment samples compared with baseline as a threshold, CD11b and CD86 positive blasts increased in bone marrow aspirates at 1 or more time points in 8 of 8 subjects and 2 of 8 subjects, respectively. Using these same criteria CD11b and CD86 positive blasts increased in peripheral blood of 7 of 9 subjects and 3 of 9 subjects, respectively. An increase in CD11b and/or CD86 occurs as early as 2 days of treatment, and as late as the last assessment at 4 weeks. A dose responsive increase could not be assessed with the 2 doses evaluated (2 mg and 4 mg).

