5.5.3. Dose Adjustment for Hematologic Toxicity

The dose of azacitidine and/or GSK2879552 may be adjusted based on neutrophil, platelet, WBC and bone marrow biopsy cellularity at baseline and nadir according to the guidelines below:

No dose adjustments are needed for anemia.

For patients with baseline (start of treatment) $WBC \geq 3.0 \times 10^9/L$, $ANC \geq 1.5 \times 10^9/L$, and platelets $\geq 75.0 \times 10^9/L$, adjust the dose as follows, based on nadir counts for any given cycle:

| Nadir Counts | | % Dose of Azacitidine/GSK2879552 to be administered |
|---------------------------|---------------------------------|---|
| Course | | - |
| ANC (x10 ⁹ /L) | Platelets (x10 ⁹ /L) | |
| <0.5 | <25.0 | 50%/50-67% |
| 0.5 –1.5 | 25.0-50.0 | 67%/67-100% |
| >1.5 | >50.0 | 100%/100% |

For patients whose baseline counts are $WBC < 3.0 \times 10^9/L$, $ANC < 1.5 \times 10^9/L$, or platelets $< 75.0 \times 10^9/L$, dose adjustments should be based on nadir counts and bone marrow biopsy cellularity at the time of the nadir as noted below, unless there is clear improvement in differentiation (percentage of mature granulocytes is higher and ANC is higher than at onset of that course) at the time of the next cycle, in which case the dose of the current treatment should be continued.

| WBC or Platelet Nadir % decrease in counts from baseline | Bone Marrow Biopsy Cellularity at Time of Nadir (%) | | |
|--|---|------------|------------|
| | 30-60 | 15-30 | <15 |
| % Dose of Azacitidine/GSK2879552 to be administered - | | | |
| 50 - 75 | 100%/100% | 50%/33-67% | 33%/25-50% |
| >75 | 75%/50-100% | 50/33-67% | 33%/25-50% |

If a nadir as defined in the table above has occurred, the next course of treatment should be given 28 days after the start of the preceding course, provided that both the WBC and the platelet counts are >25% above the nadir and rising. If a >25% increase above the nadir is not seen by day 28, counts should be reassessed every 7 days. If a 25% increase is not seen by day 42, then the patient should be treated with 50% of the scheduled dose.

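### Appendix 10 prints the platelet-improvement (HI-P) thresholds per mL, 1000-fold below the protocol's other platelet units; read literally, almost any platelet rise counts as HI

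*Protocol*

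**What the plan says.** Appendix 10 is the only place in the protocol that defines HI-P, and Section 7.4 sends the reader there for the response criteria. The HI-P entry has two limbs, both per mL:

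- an "increase of $> 30,000$ /mL (starting with $> 20,000$ /mL";
- an "increase from $< 20,000$ /mL to $> 20,000$ /mL by $> 100" percent.

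Elsewhere the protocol uses other units for blood counts:

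- The neutrophil limb in the same table cell is per microlitre: "increase of $> 100\%$ and > 500 /uL".
- Complete remission in the same table requires "Platelets ≥ 100 Gi/L".
- Section 2.2.4 reports that at 3 mg daily "the median lowest platelet count was 10 G/L (range: 9 to 15".
- Section 5.5.3 separates subjects at baseline by "platelets $\geq 75.0 \times 10^9/L".
- Inclusion criterion 9 in Section 5.1 sets a platelet floor of 10,000 with no unit, with "transfusions permitted to bring platelet count to >10,000".

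HI is a component of both response rates in Section 3.2. For Part 2, Section 9.1.2 says "Clinical activity is defined as a clinical benefit rate" and lists HI among the qualifying outcomes. The null rate is 30%, the alternative is 50%, and an arm succeeds with at least 12 responders out of 28.

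**The concern.** A threshold inside the primary endpoint is printed in a unit that does not fit the rest of the protocol. On the printed scale, HI-P asks for a rise far smaller than any platelet change discussed elsewhere in the document. The HI row also gives no minimum duration, whereas complete remission must be maintained for at least 4 weeks, and Section 9.4.1 counts HI at any time.

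The consequence differs between the two rates. ORR does not include stable disease, so every subject whose only qualifying event is a trivial platelet rise adds to it. CBR does include stable disease, so the error changes CBR only for subjects who would otherwise fail. An example is a subject with a brief rise who then progresses before the 8 weeks that stable disease requires.

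**Working it through.** **1. Unit conversion.** 1 mL = 1000 µL, and 1 x10^9/L = 1,000/µL = 1,000,000/mL.

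| Printed value | Literal, per mL | Same digits per µL |
|---|---|---|
| 30,000 | 30,000 x 1000 = 3 x 10^7/L = 0.03 x10^9/L | 30 x10^9/L |
| 20,000 | 20,000 x 1000 = 2 x 10^7/L = 0.02 x10^9/L | 20 x10^9/L |

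The ratio is 30/0.03 = 20/0.02 = 1000.

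**2. Comparison with the protocol's other platelet values.** The complete-remission cut-off is 100, the baseline cut-off for dose adjustment is 75, and the median nadirs in Section 2.2.4 are 10 and 29, all in units of 10^9/L. Values of 30 and 20 belong to that range; 0.03 and 0.02 do not.

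**3. First limb taken literally.** A rise of 1 x10^9/L is 1,000,000/mL, and 1,000,000/30,000 = 33.3. The smallest whole-unit rise on the G/L scale is therefore about 33 times the required increase.

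**4. Second limb taken literally.** This step assumes that the unitless entry floor of 10,000 means per µL. The floor is then 10 x10^9/L = 10,000,000/mL, and 10,000,000/20,000 = 500. A subject at the floor already stands at 500 times the 20,000/mL starting value. The second limb is practically unreachable and every eligible subject falls under the first.

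**5. The design that HI feeds into.** Section 9.2.1 states a type I error of 0.099 and 81% power. The check is an exact recursion, P_n(k) = (1 - p) P_(n-1)(k) + p P_(n-1)(k - 1). At each Table 5 look (n = 10, 12, ..., 28) the probability at or below the futility boundary is removed.

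- p = 0.30: probability of success 0.0991 (stated 0.099); stopping 1 - 0.0991 = 0.9009 (stated 0.90).
- p = 0.50: probability of success 0.8174 (stated 81%); stopping 1 - 0.8174 = 0.1826 (stated 0.183).
- The continuation probabilities agree with Table 5 at every look from 10 to 26.

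The stated operating characteristics therefore hold, provided that the endpoint is scored as the 30% and 50% rates assume.

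**6. Sensitivity, by assumption only.** Let f be the fraction of subjects who would otherwise fail CBR but are scored HI-P only because of the literal unit. The documents give no value for f. With a true CBR of 0.30, the scored rate is 0.30 + 0.70f. The same recursion gives:

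| f (assumed) | Scored CBR | Probability of success |
|---|---|---|
| 0 | 0.30 | 0.099 |
| 0.1 | 0.37 | 0.31 |
| 0.2 | 0.44 | 0.61 |
| 0.3 | 0.51 | 0.84 |
| 0.5 | 0.65 | 0.99 |

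The table shows how sensitive the 12-of-28 rule is to misclassification. It does not estimate how much misclassification would occur.

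**The case against.** **The unit may be a misread character.** The protocol text was converted from PDF, other parts of the Appendix 10 table are visibly damaged, and a Greek mu can come through as an m. All the per-mL entries are in the HI-P lines, so a single glyph problem would repeat. The per-µL neutrophil entry is written with a plain u and does not prove that a mu would have survived. This objection stands as a reason to look at the PDF. It does not remove the point, because the unit is printed the same way four times and a different unit appears in the same cell.

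**Assessors would probably not apply it literally.** The protocol ties response to the 2006 IWG criteria, and the complete-remission row shows the intended scale. This stands too, and it limits the practical effect. A primary-endpoint definition should still not depend on readers correcting it silently.

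**Stronger readings that the documents do not support:**

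- A reader might put a number on chance HI by treating baseline and later counts as interchangeable. Sections 2.2.4 and 4.11.1 describe dose-dependent platelet decline on GSK2879552, Section 4.11.1 adds thrombocytopenia from azacitidine, and Section 5.5.1.1 allows transfusions throughout. Counts are not interchangeable under those conditions.
- A reader might set the frequency of any platelet rise directly against the 30% null. That ignores the overlap with stable disease in CBR.
- A reader might conclude that the 12-of-28 rule is itself wrong. Its stated error rates reproduce.
- A reader might treat the missing number in the erythroid transfusion limb as a second error. It may have been lost in the conversion and is not relied on here.

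**Conclusion.** The point holds as a unit error in a definition that the primary endpoint uses. As printed, the HI-P thresholds are 0.03 and 0.02 x10^9/L, exactly 1000-fold below the scale of every other platelet value that carries a unit. Taken literally, almost any platelet rise is HI. It therefore counts in ORR, and in CBR for subjects who do not already qualify through stable disease or another component.

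The conclusion that the second limb is practically unreachable rests on reading the entry floor of 10,000 per µL. That is the only plausible reading, but the protocol does not print the unit. The whole point is conditional on the source PDF showing mL.

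No figure for the inflation of CBR or ORR follows from the documents. It depends on the rate of incidental platelet rises, which is not given, and on literal application, which is unlikely. The error should be corrected because it changes who counts as a success under the written rule, not because a particular bias has been shown.

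**What to change.** Check the HI-P lines of Appendix 10 in the source PDF. If they read per µL there, nothing needs changing. If they read per mL, restate both limbs with the same digits on the platelet scale of the rest of the table:

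- first limb: a rise of more than 30 x10^9/L from a start above 20 x10^9/L;
- second limb: from below to above 20 x10^9/L, by more than 100%.

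Printing the unit beside the entry floor of 10,000 in Section 5.1, and in its copy in the synopsis, would remove the remaining ambiguity.

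The cost is one corrected line in Appendix 10 plus the optional unit. The sample size, the Table 5 boundaries and the data collected do not change. If HI-P has already been scored for any subject, confirm which unit was used.
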